3.2. Exposure to light flashes

In theory, visual flicker may induce epileptiform EEG activity and seizures. Indeed, flashing lights of certain frequencies can be used to intentionally elicit seizures in certain susceptible patients.

- According to a review for the Epilepsy Foundation of America Working Group published in 2005³⁹:
 - The estimated prevalence of seizures from light stimuli is about 1 per 10,000, or 1 per 4,000 individuals age 5-24 years.
 - People with epilepsy have a 2-14% chance of having seizures precipitated by light or pattern.
 - Intensities of 0.2-1.5 million candlepower are in the range to trigger seizures; frequencies 15-25Hz are most provocative, but the range is 1-65Hz; red color is a factor.
- Precautions taken in this study to reduce the risk of inducing seizures:
 - Several studies using visual flicker in humans have already been published^{1,13,17-24}. Our project will expose human patients to similar stimuli and is not expected to present a risk that would be higher than in those studies, for the general population.
 - In their study, Wolf and Goosses⁴⁰ report 103 out of 1062 patients with epilepsy in their cohort to be photosensitive (i.e. having seizure or abnormal activity induced by photostimulation). Among patients with localization-related (focal) epilepsies in their cohort, only 2.7% showed photosensitivity. Based on this study and expert opinion, we expect that when photic stimulation triggers a seizure in epileptic patients, it typically occurs in patients that have a generalized type of epilepsy disorder. Most of our patients are highly selected to have focal epilepsy characterized by seizures starting in specific brain locations. Thus, we estimate that the risk of photic-induced seizures is very low in our patient population compared to the overall epilepsy patient population, except for: 1) rare patients whose epilepsies start in the occipital region or 2) rare cases where it is suspected that the patient may have a generalized type of epilepsy disorder. For such patients (1 and 2 above), we will first check that they have not been shown to be photosensitive; we will then coordinate with the clinical team to determine, on a patient-by-patient basis, whether exposure to visual flicker or individual light flashes is contraindicated with respect to clinical goals. Causing a photic-induced seizure in such patients, while not necessarily desirable for research, may provide additional information useful to the clinical team.
 - Most of our patients have already been tested for photosensitivity and photic-induced seizures during their phase I (scalp EEG) long term video seizure monitoring, at photic stimulation frequencies of 1-21Hz (for 10s trains). We will check each patient's health records to see whether they have been tested.

Patients that have been identified as photosensitive or susceptible to photic-induced seizures will not be enrolled in this study.

- Before running an experiment involving exposure to light flashes (individual flashes at around 1Hz or less, or higher frequency flicker), we will consult with the clinical team to confirm that the patient is not suspected to be sensitive to photic-induced seizures.
- For patients selected for the study, the researcher will be in the patient room anytime exposure to light flashes is administered, and available to alert the clinical team in case of a clinical seizure. Moreover, the clinical staff (such as ICM technologists) will be monitoring the patient for signs of clinical seizure, as per usual. If a clinical seizure occurs at any point during the experiment, the experiment will be stopped and the patient will be treated by the clinical staff as per usual.
- For any experiment involving exposure to light flashes, we will first choose an intensity of light that is comfortable to the subject, then test the subject for any evidence of seizure in response to the range of visual flicker or individual light flashes' parameters to which we would expose the subject.

Flicker (including in given cases invisible flicker) may trigger a range of temporary symptoms that do not represent an immediate health risk to the patient but may induce pain or discomfort, such as:

- Psychogenic, nonepileptic seizures (PNES). If a patient has a pre-existing diagnosis of PNES, we will check whether they have received photic stimulation in the clinic, and whether such stimulation triggered an episode of PNES; we will also consult the clinical team's opinion on whether sensory stimulation constitutes a risk to trigger PNES in that patient. Patients considered at risk of PNES triggered from such sensory stimulation will be excluded from the study.
- "migraine or severe paroxysmal headache often associated with nausea and visual disturbances"⁴¹.
- "malaise, headache, and impaired visual performance"⁴¹.
- "increased repetitive behavior among persons with autism"⁴¹. Patients with a pre-existing diagnosis of autism will be excluded from this study.
- "asthenopia, including eyestrain, fatigue, blurred vision, conventional headache, and decreased performance on sight-related tasks"⁴¹.
- "panic attack, anxiety, and vertigo"⁴¹.
- "decreased performance on certain tasks"⁴¹.
- "increased heart rate in agoraphobic individuals"⁴¹.
- Discomfort.

A published human study¹³ involved audiovisual stimulation for 36 minutes at 5.5Hz, 14Hz, or exposure to white noise, using a device similar to one of the devices (customized DAVID devices) we will be using. Thus, we expect to find similar minimal levels of discomfort as were found in this study. At any point in the experiment, if any of the issues mentioned above manifest, or if the patient complains of discomfort, we will modify parameters of the light flicker or individual

light flashes (such as flicker frequencies tested, light intensity). If issues persist, we will discontinue exposure to light flashes for this subject.

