2.2.8. Memory consolidation experiment

To determine whether audiovisual flicker impacts memory consolidation, subjects may go through the following experimental paradigm or a similar one, based on Roberts et al.'s (2018)¹³ experiment (Figure 5).

Patients will view 4 series of words or images. In 2 of these series, they will be asked for each word or image whether it refers to a living thing, while in the other 2 series, they will be asked whether each word or image refers to something that is man-made. This will be followed by a 36-minutes period of exposure to audiovisual flicker (either random or 5.5Hz or 40Hz, via the customized DAVID device). Finally, they will undergo an unexpected test of memory for the words or images they've been exposed to (item recognition), as well as the associated contextual sorting they had to perform (alive vs man-made, i.e. source recognition).

For this experiment, depending on his or her choice, a patient may go through the task more than once on different days, being exposed to a different condition each time (random, 5.5Hz, or 40Hz audiovisual flicker). This would allow us to compare the effects of specific frequencies of audiovisual flicker on memory, in the same patients.

[figure not shown]

Figure 5: experimental paradigm from Roberts et al. (2018). In our experiment, we may use images instead of words, and patients will be tested for effects of either random, 5.5Hz or 40Hz audiovisual flicker on memory. In case a patient were to be tested for the effects of more than one type of sensory flicker, he or she would be tested for each type of sensory flicker on different days.

The anticipated duration of this experiment is about 120min for each day.

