3.3. Exposure to auditory stimuli

Seizures induced by auditory stimuli are extremely rare and usually well-known to such a patient and their clinical team⁴². As in the case of exposure to light flashes (cf above), the subject will be monitored by both researcher and clinical staff for signs of a clinical seizure. If such signs are noted, the experiment will be stopped and patient treated as per usual.

Exposure to auditory stimuli might theoretically induce discomfort. We will first find a volume of sound that is comfortable to the patient. During an experiment, if the patient complains of discomfort, we will modify parameters of the auditory stimuli (such as flicker frequencies tested, sound volume). If discomfort persists, we will discontinue exposure to auditory stimuli for this patient.

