4.1. Inclusion criteria

- Adult (>18 years, regardless of gender, race or ethnicity).
- To be implanted with intracranial depth or grid/strip electrodes for surgical evaluation.
- Patient was not shown, during phase I seizure monitoring, to exhibit abnormal EEG activity in response to photic stimulation, and is not clinically suspected to be susceptible to photic-induced seizures.
- Patient has no pre-existing diagnosis of autism.
- Patient is not considered at risk for psychogenic nonepileptic seizures (PNES) triggered by sensory stimulation.
- Fluent in English.
- Able to understand an informed consent (comprehend potential risks and benefits).
- Give written and verbal informed consent to all experiments patient would participate in.

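### After a first light-triggered psychogenic nonepileptic seizure (PNES) that resolves, Section 3.2 as worded lets light flicker continue at changed settings, and nothing requires PNES risk to be judged again first

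*Combined protocol and SAP*

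**What the plan says.** Section 3.2 (Exposure to light flashes) gives nine kinds of temporary symptom that flicker may trigger and describes them as posing no immediate health risk. PNES comes first. Under that item, a patient who already has a PNES diagnosis is checked for earlier reactions to photic stimulation, the clinical team is asked for its opinion, and the item ends: "Patients considered at risk of PNES triggered from such sensory stimulation will be excluded from the study". Section 4.1 makes the same point an inclusion criterion: "Patient is not considered at risk for psychogenic nonepileptic seizures (PNES) triggered by sensory stimulation".

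The closing paragraph of Section 3.2 sets the response during an experiment: "if any of the issues mentioned above manifest, or if the patient complains of discomfort, we will modify parameters of the light flicker". It continues: "If issues persist, we will discontinue exposure to light flashes for this subject". No item on the list is exempted.

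Section 3.2 also has a separate stop rule: "If a clinical seizure occurs at any point during the experiment, the experiment will be stopped". Before a light-flash experiment, "we will consult with the clinical team to confirm that the patient is not suspected to be sensitive to photic-induced seizures", and the subject is first tested for evidence of seizure over the planned stimulation settings.

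**The concern.** A PNES set off by light flicker is direct evidence of the susceptibility that Sections 3.2 and 4.1 are meant to keep out of the study. Yet the symptom rule treats it like eyestrain or headache: change the settings, and stop only if the problem continues. A single episode that ends by itself does not obviously persist, so the rule as written allows more exposure.

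If the PNES exclusion is read as applying throughout participation, staff have two instructions that point in different directions and no step that says which governs. If it is read as an entry check only, nothing on study replaces it. What is at stake is a further episode or discomfort in a patient who has just shown the reaction. No outcome measure or analysis depends on it.

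**Working it through.** This is a question of wording, and the plan states no figure to reproduce. The check is to set the rules beside one case: a patient with no known PNES risk has a first PNES during light flicker, and it resolves.

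1. **Does the symptom rule cover PNES?** Yes. It refers back to the whole list, PNES is item 1 of 9, and nothing removes it. Two of the nine items, PNES and the autism item, also carry an exclusion. Autism is a pre-existing diagnosis, so PNES is the only one of the two that can first appear as an event during a session.

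2. **Does anything re-apply the PNES exclusion?** The check described in Section 3.2 starts from a pre-existing diagnosis. The exclusion sentence has no time limit, but no step directs anyone back to it after an on-study event.

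3. **Do the other safeguards fill the gap?**

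| Safeguard | Section | What it leaves open |
|---|---|---|
| Stop for a clinical seizure | 3.2 | Does not say whether PNES counts; sets no condition on later sessions |
| Seizure test before a light experiment | 3.2 | Looks for seizure; PNES not named |
| Clinical-team consultation before a light experiment | 3.2 | Asks about photic-induced seizures; PNES not named |
| Safety-monitor review of every adverse event | 6.1 | Resumption does not wait for it |
| Prompt report to the monitor if the event involved a seizure or was unanticipated | 6.2 | PNES is anticipated in 3.2, so this depends on whether it counts as a seizure |
| Withdrawal by researchers, safety monitor or attending neurologist | 4.5, 6.2 | A power, not a required step |

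Each may help in practice. None names PNES or withholds flicker until PNES risk has been re-judged.

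4. **Does the rule reach sound?** No. Section 3.3 changes auditory settings only for discomfort, and on signs of a clinical seizure it says "If such signs are noted, the experiment will be stopped and patient treated as per usual". The conflict in the text is therefore confined to light, including the light part of audiovisual flicker.

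5. **How much exposure could follow?** In the consolidation experiment (Section 2.2.8), "a patient may go through the task more than once on different days, being exposed to a different condition each time". There are 3 conditions (random, 5.5 Hz, 40 Hz) of 36 minutes each:

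- all three conditions: 3 × 36 = 108 minutes;
- left after an event in the first session: (3 − 1) × 36 = 72 minutes.

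The 72 minutes is a ceiling for that experiment. It assumes that the patient chooses all three conditions, that the event falls in the first session, and that neither staff nor patient intervenes.

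**The case against.** The best reply is that the specific sentence should govern the general one. The PNES exclusion has no time limit and speaks of exclusion from the study, whereas the sentence on known photosensitive patients speaks of not enrolling them. The symptom rule sits in a paragraph that expects minimal discomfort. On that reading the fault is a missing cross-reference. In addition, staff watching for a clinical seizure would probably stop for anything resembling one. If PNES counts as involving a seizure, the safety monitor promptly reviews EEG, video and the medical record, and can withdraw the patient. These are inpatients under round-the-clock monitoring.

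Much of this stands, and it is why the point is minor. It does not remove the point. The continuing reading has to be inferred, the status of PNES under the seizure rules is undefined, and no review has to come before the next exposure.

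A reader might infer more than the documents support:

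- **That patients are unprotected after a PNES.** The safeguards in the table are real, and several would probably act.
- **That the defect covers all sensory flicker.** The symptom rule in Section 3.2 governs light only.
- **That the electrical-stimulation rule shows a plainly stricter standard.** Section 3.1 does halt and assess at a first afterdischarge, but testing then resumes at a current 25-30% lower, and sessions are cancelled if afterdischarges recur. That is close to the same modify-then-stop pattern.
- **That 72 minutes is an expected exposure.** It is an upper bound and says nothing about likelihood.

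**Conclusion.** The point holds as a minor safety-wording gap. Taken literally, the symptom rule in Section 3.2 permits further light exposure at changed settings after a first light-triggered PNES that resolves. This is in tension with the PNES exclusion in Sections 3.2 and 4.1, and no step requires the risk to be re-judged first.

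The conclusion rests on reading the rule's reference to the listed issues as including its first item, and on finding no provision elsewhere that makes resumption conditional on a PNES assessment. The frequency cannot be estimated, because the documents give no PNES rate. With known at-risk patients screened out, events should be few among the roughly 100 patients planned (Section 4). The expected harm is temporary and limited.

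**What to change.** Take PNES out of the rule at the end of Section 3.2 that answers symptoms by changing the settings, and add two sentences to this effect:

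> A PNES or PNES-like event during flicker stops the experiment. Flicker resumes only if the clinical team reassesses the patient against the PNES criterion in Section 4.1 and finds that the patient still meets it.

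Because that criterion refers to sensory stimulation in general, the reassessment may reasonably cover auditory flicker as well, although the conflict in the text concerns light alone.

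The cost is a short protocol amendment, a brief consultation when such an event occurs, and the occasional loss of a participant's remaining flicker sessions.

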3.3. Exposure to auditory stimuli

Seizures induced by auditory stimuli are extremely rare and usually well-known to such a patient and their clinical team⁴². As in the case of exposure to light flashes (cf above), the subject will be monitored by both researcher and clinical staff for signs of a clinical seizure. If such signs are noted, the experiment will be stopped and patient treated as per usual.

Exposure to auditory stimuli might theoretically induce discomfort. We will first find a volume of sound that is comfortable to the patient. During an experiment, if the patient complains of discomfort, we will modify parameters of the auditory stimuli (such as flicker frequencies tested, sound volume). If discomfort persists, we will discontinue exposure to auditory stimuli for this patient.

3.4. Memory experiments

The subject could experience eye strain from looking at words or images on a computer screen for extended periods of time, and could experience anxiety from memory testing. In our previous studies, such complaints are extremely rare and minimal.

3.5. Spatial navigation task

The subject may here also experience eye strain or nausea from navigating in a virtual environment for extended periods of time, and could experience anxiety from memory testing. In our previous studies, such complaints were extremely rare and minimal. They may also experience frustration or fatigue from memory testing. Moreover, it is possible that navigating in the virtual environment, while being exposed to visual and/or auditory flicker simultaneously, might induce similar symptoms or discomfort. The patient will be monitored at all times, and the stimulation parameters (brightness, volume) will be modified if the patient complains of any symptoms or discomfort, or the experiment will be stopped altogether if those changes do not resolve the issue. Moreover, special care will be given to the wellbeing of the subject and testing will be stopped at the subject's request.

3.6. Custom cable and splitter box

Custom cables and splitter boxes have been developed with Blackrock Microsystems to split the signal between the clinical EEG system and the Blackrock neural recording and stimulation devices. These components have been extensively tested to ensure that they provide uninterrupted physiological monitoring capabilities. However, as with any component, there is a very small risk of failure.

Cable failure does not put the subject at risk of injury. However, it does introduce the risk of data loss. If the cable fails during the time when the subject is not having a seizure, then there is no risk to the subject. However, if the cable fails while the subject is having a clinically necessary seizure then this may extend the subject's length of stay in the Epilepsy Monitoring Unit (EMU) until the subject has another seizure that can be localized. The risk of a cable failure that extends

the subject's stay in the EMU is anticipated to be very small. In addition, there is no reason to expect that the risk of the Blackrock cable failure is any greater than the risk of the standard clinical cable failing.

3.7. Breach of confidentiality

The link between subject identifying information, such as subject's name, and assigned study subject identifier, will be saved on a PHI-compliant server that only research personnel may access. Furthermore, data will be stripped of PHI as much as possible and as soon as possible. Data with limited subject PHI will be stored on PHI-compliant servers that only research personnel may access. No identifying information will be used in any publication that results from this research. Behavioral data are only coded with an indirect identifier and date of research testing, and stored on a secure, password protected laptop or computer and stored later on HIPAA compliant servers that only research personnel may access. Should at any time a breach of confidentiality be detected, the patient(s) will be notified directly, and we will undertake a thorough reevaluation of methods to protect patient confidentiality.

De-identified data from this study (data that has been stripped of all information that can identify the subjects) may be placed into public databases where, in addition to having no direct identifiers, researchers will need to sign data use agreements before accessing the data. We will remove or code any personal information that could identify the subject before information is shared. This will ensure that, by current scientific standards and known methods, it is extremely unlikely that anyone would be able to identify the subject from the information we share.

Data from this study may be useful for other research being done by investigators at Emory or elsewhere. To help further science, we may provide subject deidentified data to other researchers. If we do, we will not include any information that could identify the subject. If data is labeled with a subject's study ID, we will not allow the other investigators to link that ID to the subject's identifiable information.

3.8. Sharing of results with participants

In general, we will not give the subject any individual results from the study of the data that is produced from their participation. If we find something of urgent medical importance to them, we will inform them, although we expect that this will be a very rare occurrence.

3.9. Potential benefit to participants

There is no direct benefit to participants from this study, except possibly entertaining them during their hospital stay. Subjects will not be compensated for participating in this study.

3.10. Cost to participants

There will be no costs to the subject for participating in this study. They will not be charged for any of the research activities.

4. PARTICIPANT RECRUITMENT

We aim to include, across all experiments, about 100 adult patients (most patients will only participate in one or a few of the experiments) with pharmaco-resistant epilepsy in whom intracranial depth or grid/strip electrodes are implanted in order to determine the area of seizure onset for possible surgical resection. We anticipate having access to an adequate sample size to attain significant preliminary data in one year. Between two neurosurgeons, our center implants >50 epilepsy patients per year for intracranial monitoring. Approximately 90% of these patients will meet all inclusion criteria.

